5.6. Protocol Deviations

The following describes any protocol deviations that relate to the statistical analyses or populations:

5.6.1. Deviations Assessed Prior to Randomization

Subjects who do not meet the inclusion / exclusion criteria will not be included in the evaluable immunogenicity population as specified in [Section 5.2](#).

5.6.2. Deviations Assessed Post-Randomization

The full list of protocol deviations (including protocol violations) for the study report(s) will be compiled prior to database release at the visit corresponding to the primary analysis and final analysis. The subjects with major protocol deviations, as determined by Medical Monitor, will be excluded from the evaluable immunogenicity population.

6. ENDPOINTS AND COVARIATES

6.1. Immunogenicity Endpoints

The lower limit of quantitation (LLOQ) for primary test strain **CCI** (A22) is 1:16. The LLOQ for each of the other 3 primary test strains is 1:8.

6.1.1. Primary Immunogenicity Endpoints

- *Proportions of subjects achieving an hSBA titer \geq LLOQ 1 month after the third vaccination, for each of the 4 primary MnB test strains in healthy toddlers aged 12 to <18 months at study entry.*
- *Proportions of subjects achieving an hSBA titer \geq LLOQ 1 month after the third vaccination, for each of the 4 primary MnB test strains in healthy toddlers aged 18 to <24 months at study entry.*

6.1.2. Secondary Immunogenicity Endpoints

The following endpoint will be applied to results in healthy subjects aged 12 months to <24 months (ie, both age strata combined) at study entry:

- *Proportion of subjects with hSBA titers \geq LLOQ for each of the 4 primary MnB test strains 1 month after the third vaccination with bivalent rLP2086.*

The following endpoints will be applied to results in healthy subjects aged 12 to <18 months and 18 to <24 months at study entry, and in both age strata combined:

- *Proportions of subjects with hSBA titers \geq LLOQ for each of the 4 primary MnB test strains at 1 month after the second vaccination with bivalent rLP2086 and 6, 12, 24, 36, and 48 months after the third vaccination with bivalent rLP2086.*
- *Proportions of subjects with hSBA titers \geq LLOQ, $\geq 1:4$, $\geq 1:8$, $\geq 1:16$, $\geq 1:32$, $\geq 1:64$, and $\geq 1:128$ for each of the 4 primary MnB strains at each applicable blood sampling visit.*
- *hSBA GMTs for each of the 4 primary test strains at each applicable blood sampling visit.*

6.1.3. CCI [REDACTED]

CCI [REDACTED]

[REDACTED]

[REDACTED]

[REDACTED]

[REDACTED]

[REDACTED]

[REDACTED]

CCI [REDACTED]

[REDACTED]

[REDACTED]

[REDACTED]

[REDACTED]

6.2. Safety Endpoints

6.2.1. Primary Safety Endpoints

The following endpoints will be applied to results in healthy toddlers aged 12 to <18 months and in healthy toddlers aged 18 to <24 months at study entry, and in both age strata combined:

- *Percentages of subjects reporting local reactions (tenderness, redness, and swelling) and by severity after each vaccination visit.*
- *Percentages of subjects reporting systemic events (fever, decreased sleep, increased sleep, decreased appetite, and irritability) by severity after each vaccination visit.*
- *Percentages of subjects reporting the use of antipyretic medication after each vaccination visit.*
- *Percentages of subjects with at least 1 SAE during the following time periods:*
 1. *30 Days after each vaccination.*
 2. *30 Days after any vaccination.*
 3. *During the vaccination phase (from the first study vaccination [Visit 1] through month after the last study vaccination [Visit 7]).*
 4. *During the follow-up phase (from 1 month after the last study vaccination [Visit 7] through 6 months after the third study vaccination [Visit 8]).*
 5. *Throughout the SAE collection period (from the first study vaccination [Visit 1] through 6 months after the third study vaccination [Visit 8]).*

- *Percentages of subjects with at least 1 MAE occurring during the following time periods:*
 1. *30 Days after each vaccination.*
 2. *30 Days after any vaccination.*
 3. *During the vaccination phase (from the first study vaccination [Visit 1] through 1 month after the last study vaccination [Visit 7]).*
 4. *During the follow-up phase (from 1 month after the last study vaccination [Visit 7] through 6 months after the third study vaccination [Visit 8]).*
 5. *Throughout the AE collection period (from the first study vaccination [Visit 1] through 6 months after the third study vaccination [Visit 8]).*
- *Percentages of subjects with at least 1 NDCMC occurring during the following time periods:*
 1. *30 Days after each vaccination.*
 2. *30 Days after any vaccination.*
 3. *During the vaccination phase (from the first study vaccination [Visit 1] through 1 month after the last study vaccination [Visit 7]).*
 4. *During the follow-up phase (from 1 month after the last study vaccination [Visit 7] through 6 months after the third study vaccination [Visit 8]).*
 5. *Throughout the AE collection period (from the first study vaccination [Visit 1] through 6 months after the third study vaccination [Visit 8]).*
- *Percentages of subjects with at least 1 AE occurring during the following time periods:*
 1. *30 Days after each vaccination.*
 2. *30 Days after any vaccination.*
 3. *During the vaccination phase (from the first study vaccination [Visit 1] through 1 month after the last study vaccination [Visit 7]).*
- *Percentages of subjects reporting at least 1 immediate AE after each vaccination.*

These endpoints are detailed in below [Section 6.2.2](#) and [Section 6.2.3](#) based on data sources. The details for each analysis interval are described in these sections.

6.2.2. Reactogenicity Data

Reactogenicity data is solicited adverse events (AEs). The reactogenicity data collected from e-Diary will be: local reactions (redness, swelling, and tenderness at injection site), systemic events (loss of or decreased appetite, drowsiness [increased sleep], and irritability [fussiness]), temperature and use of antipyretic medication.

The e-Diary will record reactogenicity data from day 1 to day 7 for each vaccination. The analysis interval for reactogenicity data after each vaccination will be ‘any day 1-7’ which includes data from day 1 to day 7. The day of vaccination is considered as day 1.

Table 3. Analysis Interval for Reactogenicity Data

#	Analysis Interval	Analysis Population	Interval Start date (inclusive)	Interval Stop (inclusive)
1	vaccination 1	Vax 1 Safety	Vax 1 date	Vax 1 date + 6 days (or until resolved day)
2	vaccination 2	Vax 2 Safety	Vax 2 date	Vax 2 date + 6 days (or until resolved day)
3	vaccination 3	Vax 3 Safety	Vax 3 date	Vax 3 date + 6 days (or until resolved day)
4	any vaccination	Safety	Vax 1, Vax 2, or Vax 3	Vax 1, Vax 2, or Vax 3+ 6 days (or until resolved day)

6.2.2.1. Local Reactions Endpoints

The local reactions collected from the e-Diary will be: tenderness at injection site, redness, and swelling.

Local Reaction Presence (Proportion of subjects reporting each local reaction)

For each local reaction, the derivation of whether or not the specific reaction occurred on each day and ‘any day 1-7’ will be made. The variable will be calculated for each vaccination as well as overall reactions for any vaccination. The derivation of this variable is given in Table 4 below.

Table 4. Derived Variables for Local Reactions

Variable	Yes (1) ^a	No (0) ^b	Missing (.)
Any day 1-7	Parent/legal guardian reports the reaction as ‘mild’ ‘moderate’ or ‘severe’ on any day 1-7	Parent/legal guardian reports the reaction as ‘none’ on all 7 days or as a combination of ‘none’ and missing on all 7 days.	Parent/legal guardian reports the reaction as missing on all 7 days.

- a. For redness and swelling, ‘mild’, moderate’, and ‘severe’ categories were based on the caliper size reported from e-Diary
- b. For redness and swelling, ‘none’ means 0 caliper units reported in the e-Diary

Maximum Severity for Local Reaction

A caliper is used to measure the redness or swelling area. Caliper units are converted to centimeters according to 1 caliper unit = 0.5 centimeters. The grading of local reactions is listed below in Table 5 and Table 6.

Table 5. Grading of Redness and Swelling

Grades	Measurement
None	0 cm (0 caliper units)
Mild	0.5 to 2.0 cm (1 to 4 caliper units)
Moderate	2.5 to 7.0 cm (5 to 14 caliper units)
Severe	>7.0 cm (>14 caliper units)

Table 6. Grading of Tenderness

Grades	
Mild	Hurts if gently touched (eg, subject whimpers, winces, protests, or withdraws)
Moderate	Hurts if gently touched with crying
Severe	Causes limitation of limb movement

The maximum severity (highest grading) of each local reaction within 7 days of vaccination will be derived for each vaccination as well as any vaccinations. The maximum severity will be derived as follows:

= •, if values are missing for all days 1-7;

= 0, if the subject reports all reactions as ‘None’ or a combination of missing and none for all days 1-7

= *highest grade* (maximum severity) within 7 days of vaccination, if the answer is not ‘None’ for at least 1 day;

Duration of Each Local Reaction

For subjects experiencing any local reactions (or those with derived reaction presence in Table 4), the maximum duration (last day of reaction –first day of reaction +1) will be derived for each vaccination. Resolution of the event is the last day in which the event is recorded in the e-Diary or the date the event ends if it is unresolved during the subject diary-recording period, unless chronicity is established.

In summary, the following variables will be derived for local reaction:

1. Each local reaction on each day (up to day 7) after each vaccination.
2. Each local reaction on ‘any day 1-7’ after each vaccination and any vaccination.
3. Maximum severity of each local reaction on ‘any day 1-7’ after each vaccination and any vaccination.
4. Maximum duration of each local reaction after each vaccination.
5. Any local reaction on ‘any day 1-7’ after each vaccination and after any vaccination.

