2.2.2. Primary Safety Endpoints

The following endpoints will be applied to results in healthy toddlers aged 12 to <18 months and in healthy toddlers aged 18 to <24 months at study entry, and in both age strata combined:

- Percentages of subjects reporting local reactions (tenderness, redness, and swelling) and by severity after each vaccination visit.
- Percentages of subjects reporting systemic events (fever, decreased sleep, increased sleep, decreased appetite, and irritability) by severity after each vaccination visit.
- Percentages of subjects reporting the use of antipyretic medication after each vaccination visit.
- Percentages of subjects with at least 1 SAE during the following time periods:
 - 30 Days after each vaccination.
 - 30 Days after any vaccination.
 - During the vaccination phase (from the first study vaccination [Visit 1] through 1 month after the last study vaccination [Visit 7]).
 - During the follow-up phase (from 1 month after the last study vaccination [Visit 7] through 6 months after the third study vaccination [Visit 8]).

- Throughout the SAE collection period (from the first study vaccination [Visit 1] through 6 months after the third study vaccination [Visit 8]).
- Percentages of subjects with at least 1 MAE occurring during the following time periods:
 - 30 Days after each vaccination.
 - 30 Days after any vaccination.
 - During the vaccination phase (from the first study vaccination [Visit 1] through 1 month after the last study vaccination [Visit 7]).
 - During the follow-up phase (from 1 month after the last study vaccination [Visit 7] through 6 months after the third study vaccination [Visit 8]).
 - Throughout the AE collection period (from the first study vaccination [Visit 1] through 6 months after the third study vaccination [Visit 8]).
- Percentages of subjects with at least 1 NDCMC occurring during the following time periods:
 - 30 Days after each vaccination.
 - 30 Days after any vaccination.
 - During the vaccination phase (from the first study vaccination [Visit 1] through 1 month after the last study vaccination [Visit 7]).
 - During the follow-up phase (from 1 month after the last study vaccination [Visit 7] through 6 months after the third study vaccination [Visit 8]).
 - Throughout the AE collection period (from the first study vaccination [Visit 1] through 6 months after the third study vaccination [Visit 8]).
- Percentages of subjects with at least 1 AE occurring during the following time periods:

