6.3. Unscheduled Visits

The parent(s)/legal guardian will be requested to contact the study staff if the subject experiences a severe redness or swelling at the injection site (>14 caliper units) or a temperature $\geq 39.0^{\circ}$ C (102.2° F) in the 7 days after vaccination. If the parent(s)/legal guardian does not contact the site, the investigator is required to contact the parent(s)/legal guardian as soon as possible. The outcome of any contact will be recorded on the CRF. The investigator should determine if the subject requires an unscheduled visit. If the unscheduled visit does not take place following subject report of fever $\geq 39.0^{\circ}$ C (102.2° F) or severe redness/swelling, the reason must be documented in the CRF (for example, reaction no longer present or e-diary–entry error).

If the reaction exceeds the maximum size the caliper is able to measure (>14 caliper units), ensure the subject's parent(s)/legal guardian has also measured the maximum diameter of the redness and/or swelling at the injection site using the measuring tape/ruler provided. Ask the subject's parent(s)/legal guardian to report the maximum diameter of the redness and/or swelling at the injection site daily until the reaction becomes ≤ 14 caliper units. Record these measurements in the CRF.

At an unscheduled visit, the subject's axillary temperature should be measured and the symptom that prompted the visit should be assessed by a medically qualified member of the study staff. Findings will be recorded on the CRF including route temperature was taken. If the subject experiences any AEs, these should be recorded on the AE page.

Final Protocol Amendment 2, 19 April 2016

For the purpose of assessments performed during unscheduled visits, a medically qualified member of the study staff is a study physician or a study nurse, as applicable to the investigator's local practice.

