7.3. Electronic Diary

The subject's parent(s)/legal guardian will be issued an e-diary, based on a personal digital assistant (PDA) or equivalent technology. They will be asked to monitor and record local reactions, systemic events, and the use and type of antipyretic medication on the day of vaccination and for 7 days following each vaccination. The e-diary allows recording of these assessments only within a fixed time window, thus providing the accurate representation of the subject's experience at that time. Only the most severe rating for any of the local reactions or systemic events each day will be recorded in the e-diary. End dates of local reactions, systemic events, or use of antipyretic medications that was ongoing on the last day the diary was completed by the parent(s)/legal guardian will be collected on the CRF.

The investigator or designee must contact the parent(s)/legal guardian in order to obtain stop dates for any prompted diary/e-diary events or other AE data ongoing on the last day that the e-diary was completed. The stop dates are to be documented in the source documents and the information entered in the CRF. Data reported in the e-diary will be transferred electronically to the e-diary vendor (a trusted third party), where they will be available for review by investigators at all times via an Internet-based portal. At intervals agreed upon between the vendor and Pfizer, these data will be transferred electronically into Pfizer's database for analysis and reporting. These data do not need to be reported by the investigator on the CRF.

Investigators will be required to review the e-diary data online at frequent intervals as part of the ongoing safety review and evaluation of subject compliance. For sentinel-cohort subjects, following Vaccination 1 online review must be performed daily (see Section 7.9 Stopping Rules).

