7.9. Stopping Rules

The study stopping rules (excluding deaths) apply to bivalent rLP2086–vaccinated sentinel-cohort subjects for the post–Vaccination 1, 7-day safety period only.

Post–Vaccination 1, 7-day e-diary and AE (including deaths) data will be monitored daily during the post–Vaccination 1, 7-day safety period (including non–business days) by the investigator (or medically qualified designee) and sponsor in order to promptly identify and flag any case that potentially contributes to a stopping rule.

Cases that potentially meet stopping rule criteria will be promptly referred to the IRC for rapid evaluation. The IRC will review the case safety data and determine whether or not the case meets a stopping rule. The IRC opinion on study progression will be forwarded to the EDMC.

B1971035

Final Protocol Amendment 2, 19 April 2016

In the event that the IRC confirms that a stopping rule has been met, the following criteria will apply:

- The dose level affected by the stopping rule will PAUSE enrollment and vaccination in both sentinel age groups.
- No further study vaccinations will be administered to any subject in the PAUSED sentinel cohorts until directed to do so.
- The EDMC will convene to evaluate all available safety data and provide its recommendations to the IRC.
- For all sentinel subjects affected by a pause, all other routine study conduct activities such as ongoing data entry, reporting of AEs, subject e-diary completion, and subject follow-up, will continue during the pause.

A stopping rule will be met under the following circumstances:

- Where 2 or more subjects within an age-stratified sentinel cohort receiving the same dose level (60 μg or 120 μg) of bivalent rLP2086 develop an MAE that is similar in nature that cannot be attributed to any other cause during the 7 days following Vaccination 1.
 - ➤ E-diary data confirmed to be entered in error will not contribute towards a stopping rule.
 - ➤ Unscheduled per-protocol visits to the investigator do not fulfill this criterion unless the event that triggered an unscheduled visit meets the protocol-specified definition of an MAE.
- If any sentinel subject receiving bivalent rLP2086 develops an SAE that cannot be attributed to any other cause within 7 days following Vaccination 1.
- If death occurs in a bivalent rLP2086 recipient during the vaccination period that cannot be attributed to any other cause, or if an investigator determines that the death is related to vaccination.

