6.2.2.3. Temperature

Oral temperature will be collected in the e-Diary for 7 days (day 1 to day 7) after each vaccination. The highest temperature for each day will be recorded in the e-Diary. The protocol defines fever as an axillary temperature $\geq 38.0^{\circ}\text{C}$. Fever will be categorized according as 38.0°C to $\leq 38.4^{\circ}\text{C}$, 38.5°C to $\leq 38.9^{\circ}\text{C}$, 39.0°C to 39.4°C , 39.5°C to $\leq 40^{\circ}\text{C}$, and $>40^{\circ}\text{C}$ for a given day per Protocol.

Similar to the derivations of systemic events and local reactions, fever will be derived for:

1. Fever on each day (up to day 7) after each vaccination.
2. Fever on 'any day 1-7' after each vaccination and any vaccination.
3. Highest Fever (maximum severity) on 'any day 1-7' after each vaccination and any vaccination.
4. Maximum duration of fever after each vaccination.

Temperatures $<35.0^{\circ}\text{C}$ and $>42.0^{\circ}\text{C}$ will be excluded from the analysis.

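### The SAP does not use the CRF record that a severe redness or swelling entry, or a temperature of 39.0 °C or more, was an e-diary entry error, so the value counts in the primary safety percentages

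*SAP*

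**What the plan says.** **Endpoint.** Protocol 2.2.2 makes these primary safety endpoints: "Percentages of subjects reporting local reactions (tenderness, redness, and swelling) and by severity after each vaccination visit". Systemic events, including fever, are treated in the same way.

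**Derivation.** SAP 6.2.2.1 takes presence and severity from the parent's diary report, and grades redness and swelling from the diary caliper value. The child's grade is the highest one ("maximum severity) within 7 days of vaccination, if the answer is not" None on at least one day). SAP 6.2.2.2 and 6.2.2.3 derive systemic events and fever similarly. The only exclusion by value is in SAP 6.2.2.3: temperatures below 35.0 °C or above 42.0 °C "will be excluded from the analysis".

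**Missing data.** SAP 7.2.1 treats every item on a transmitted diary day as non-missing and plans no reactogenicity sensitivity analysis.

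**Comparisons.** SAP 8.2.5.1 plans differences, 95% CIs and p-values for severe local reactions by type, for severe systemic events by type and for high-temperature categories.

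**Entry errors.** Under Protocol 6.3, if no unscheduled visit follows a report of temperature of 39.0 °C or more or severe redness or swelling, "the reason must be documented in the CRF (for example, reaction no longer present or e-diary–entry error"). Protocol 7.9 adds, under its medically attended event (MAE) criterion: "E-diary data confirmed to be entered in error will not contribute towards a stopping rule".

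**Data path.** Protocol 7.3 says "The e-diary allows recording of these assessments only within a fixed time window". The entries go to the e-diary vendor, and then "these data will be transferred electronically into Pfizer's database for analysis and reporting". No route for correcting an entry is described.

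**The concern.** The protocol foresees that some alarming diary values will be typing mistakes. It has the site contact the family and puts the explanation on the CRF. The SAP then derives the affected endpoints from the diary alone. A temperature entered as 39.9 °C, which the site documents as a mistyped 36.9 °C, falls inside the 35.0 to 42.0 °C limits. It would put the child in the 39.5 to 40.0 °C band and in the comparison for temperatures of 39.0 °C or more.

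At stake is the accuracy of primary safety percentages that SAP 8.1.2.2 uses to decide which events may need further clinical investigation. There is also a question of process. Protocol 5.2.1.1 unblinds a subset of sponsor clinicians, clinical scientists and statisticians. If no rule is written, keeping or dropping a known false value could become a choice made with treatment assignment in view.

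**Working it through.** **Step 1. Follow one record through the plan.** Take a diary temperature of 39.9 °C on Day 2, all other days normal, no unscheduled visit, and entry error given as the CRF reason.

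- *Protocol 6.3:* the value is at least 39.0 °C, so a CRF reason is required. It states that the value is false.
- *SAP 7.2.1:* the day was transmitted, so every item on it is non-missing.
- *SAP 6.2.2.3:* 35.0 ≤ 39.9 ≤ 42.0, so the value is kept.
- *SAP 6.2.2.1 to 6.2.2.3:* the highest entry over Days 1 to 7 is 39.9 °C, so the child is a fever case in the 39.5 to 40.0 °C band.
- *SAP 8.2.5.1:* the child enters the percentage, difference, CI and p-value.

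A false redness or swelling entry above 14 caliper units follows the same path, with no value limit at all.

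**Step 2. Look for another provision that removes it.**

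- SAP 10.1.4 uses CRF data for diary events only for resolution dates and duration.
- SAP 8.2.5.1 lists severe reactogenicity data but mentions no error flag.
- SAP 8.2.5.1.1 lists children who had unscheduled visits. The entry-error reason is required when there was no visit, so these children may not appear there.

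None of these changes the percentage.

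**Step 3. Arm sizes.** Sentinel cohorts are about 33 at 2:1, so 22 and 11. Expanded cohorts are about 132 per age group at 2:1, so 88 and 44. Pooling cohorts within one age stratum (Protocol 9.2, SAP 6.4):

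- selected dose: 22 + 88 = 110, matching the figure in Protocol 9.1;
- control: 11 + 11 + 44 = 66;
- a dose studied only in the sentinel cohort: 22.

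Both strata combined, if the same dose is selected in each: 2 × 110 = 220.

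**Step 4. Illustrated effect.** The documents give no rate of entry errors, severe reactions or high fever. Assume that each error is the child's only qualifying entry, that there are no true events, and that all enrolled children have diary data. One error then adds 1/n. Intervals are 95% Clopper-Pearson.

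| Group | n | One error counted | Error removed | Points added by 1 to 3 errors |
|---|---|---|---|---|
| Selected dose, one stratum | 110 | 1/110 = 0.9% (0.02 to 5.0) | 0% (0 to 3.3) | 0.9 to 2.7 |
| Control, one stratum | 66 | 1/66 = 1.5% (0.04 to 8.2) | 0% (0 to 5.4) | 1.5 to 4.5 |
| Sentinel dose group | 22 | 1/22 = 4.5% (0.1 to 22.8) | 0% (0 to 15.4) | 4.5 to 13.6 |
| Selected dose, strata combined | 220 | 1/220 = 0.5% (0.01 to 2.5) | 0% (0 to 1.7) | 0.5 to 1.4 |

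**The case against.** **The SAP counts these values by silence.** No sentence says that confirmed errors are counted, and SAP Section 2 keeps programming rules in separate documents. That is true, but those rules are to be based on the methods in the SAP. The methods are explicit that the highest diary grade stands and every transmitted day is non-missing.

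**Using the diary as recorded is defensible and conservative.** Protocol 7.3 presents the fixed entry window as a safeguard of accuracy, and SAP 10.1.1.3 errs against the sponsor when an AE start date is missing. But here the information is not missing: the site has recorded that the value is false. Counting a false value is also conservative only when it falls in the vaccine arm. In the control arm it narrows the difference.

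**Removal works in one direction and covers few items.** This stands. The CRF reason is required only for redness or swelling above 14 caliper units and temperatures of 39.0 °C or more, and only when no visit took place. It does not reach tenderness, appetite, drowsiness or irritability. Errors that understate severity stay in, so removal can only lower the counts. In a sponsor-unblinded study that is a reason to show results both ways.

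**The comparisons are descriptive.** This also stands: no decision rule depends on them. It limits the consequence but does not make the count right.

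**Stronger readings that the documents do not support.** A reader might infer from Protocol 7.9 that the stopping rules and the SAP would report conflicting severe-event counts. They would not. The rules (deaths apart) cover rLP2086-vaccinated "sentinel-cohort subjects for the post–Vaccination 1, 7-day safety period only", and the entry-error line sits under the MAE criterion. Neither a severe diary grade nor a fever band is itself a trigger, so there is no rival count. The line shows only that the sponsor does not regard such data as valid evidence. A reader might also infer that the events are rare, so that errors would dominate. No event rate is given that would support this.

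**Conclusion.** The gap is real and should be closed. As written, the SAP counts a redness, swelling or temperature value that the CRF documents as an entry error in the primary safety percentages and their between-group statistics. For fever the gap is limited to entries from 39.0 to 42.0 °C, because higher values are already excluded.

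Its size cannot be derived from the documents. The per-error figures of 0.9, 1.5 and 4.5 points assume planned arm sizes and a child with no other qualifying entry. If the child has a genuine entry at the same grade, removing the error changes nothing in the percentage. The point concerns the accuracy of descriptive safety results. It does not bear on the immunogenicity endpoints, and it is not evidence that the stopping rules are at odds with the SAP.

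**What to change.** Add one rule to SAP 6.2.2 and 7.2.1. A redness, swelling or temperature item-day that blinded site staff have documented on the CRF as an e-diary entry error is set to missing, for that item and day only, before presence, maximum severity, fever category and duration are derived. In detail:

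- Apply the rule identically in all groups.
- Act only on the entry-error reason. A reaction that had gone by the time of contact was still a reaction and stays in.
- Accept only confirmations recorded before randomization codes are released to the site.
- Leave e-diary completion (SAP 6.3.1) on the transmitted record. Under SAP Table 4, a mix of no reaction and missing days already counts as no reaction, so the child normally stays in the denominator.
- List the affected records by group, with the reason.
- Present the as-recorded percentages alongside.

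The CRF reason is already required. Protocol 6.3 does not say that it identifies the diary item and day, so some site queries may be needed to make the link. The remaining costs are one SAP paragraph, one listing and a second set of percentages. The downside is reliance on site confirmation, which can only lower severe counts and covers only three items. The as-recorded table guards against this.
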